3.2 Duration and Study Completion Definition

The duration of the study will be event driven, and is based upon an assumption that there will be approximately 51 all-cause graft failures that will be adjudicated by the nephrology EAC. The trial will continue until 51 such events are accrued and adjudicated by the nephrology EAC. See Section 9.5.2 for additional details. However the maximum amount of time each subject will be followed in the study will be 4 years post initial treatment with investigational product. Subjects will complete visits every 6 months until the study is ended.

If a subject is discontinued from the study (not only from treatment) for any reason prior to the Month 6 follow-up Visit, every effort will be made to obtain AEs, serum BUN and Creatinine results, eGFR_{MDRD}, and a biopsy to send to the pathology and nephrology EACs for determination of TG and graft function status, respectively (see [Table 2](#) for Early Discontinuation Visit procedures). If a subject is discontinued from treatment for any reason for the remainder of a treatment cycle before receiving 7 doses, the subject will continue in the study and no Early Discontinuation Visit will be performed. In this instance, the next scheduled treatment visit in the treatment cycle should be conducted and all procedures for that visit should be performed other than those related to study drug administration, and the scheduled Day 25 post-treatment visit will follow (any remaining treatment visits for that cycle are not required). If a subject is discontinued from the study for any reason after the Month 6 visit and prior to the end of the study at 4 years, every effort will be made to obtain AEs, serum BUN and Cr and eGFR_{MDRD} results to send to the nephrology EAC for determination of graft function status (see [Table 2](#) for End of Study Visit procedures).

The subject's maximum duration of participation is expected to be approximately 4 years.

The Study Completion Date is defined as the date the final subject, across all sites, completes their final protocol-defined assessment. Please note that this includes the follow-up visit or contact, whichever is later. The Study Completion Date is used to ascertain timing for study results posting and reporting.

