4.5 Discontinuation or Withdrawal of Subjects

A subject may withdraw from the study at any time for any reason without prejudice to their future medical care by the physician or at the institution. The investigator or sponsor may withdraw the subject at any time (eg, in the interest of subject safety). The investigator is encouraged to discuss withdrawal of a subject from the study with the medical monitor when possible.

If a subject is discontinued from the study (not only from treatment) for any reason prior to the Month 6 follow-up Visit, every effort will be made to obtain AEs, serum BUN and Cr results, eGFR_{MDRD}, and a biopsy to send to the pathology and nephrology EACs for determination of TG and graft function status, respectively (see Table 2 for Early Discontinuation Visit procedures). If a subject is discontinued from treatment for any reason for the remainder of a treatment cycle for before receiving 7 doses, the subject will continue in the study and no Early Discontinuation Visit will be performed. In this instance, the next scheduled treatment visit in the treatment cycle should be conducted and all procedures for that visit should be performed other than those related to study drug administration, and the scheduled Day 25 post-treatment visit will follow (any remaining treatment visits for that cycle are not required). If a subject is discontinued from the study for any reason after the Month 6 visit and prior to the end of the study at 4 years, every effort will be made to obtain AEs, serum BUN and Cr and eGFR_{MDRD} results to send to the nephrology EAC for determination of graft function status (see Table 2 for End of Study Visit procedures).

Whenever possible and with the consent of the subject, the investigator will attempt to obtain information on graft and subject survival status from discontinued subjects at remaining scheduled assessment times through Month 48. The reason for termination, date of stopping investigational product, and the total amount of investigational product taken must be recorded in the case report form (CRF) and source documents.

Subjects who discontinue will not be replaced. Approximately 112 eligible subjects with biopsy-proven AMR will be randomized to provide 56 subjects per treatment arm. Additional eligible subjects may be enrolled based on the interim data analysis of the first 30 subjects who complete the Month 6 TG assessment (Section 9.5.1).

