6.2.3 Dosing

Eligible subjects in this study will receive a total of 7 doses of investigational product over a 13-day period: an initial 100 mL IV infusion containing 5000 U CINRYZE or placebo (100 mL 0.9% sodium chloride for infusion) on Day 1, followed by 2500 U of CINRYZE in 100 mL of IV infusion or placebo (100 mL 0.9% sodium chloride for infusion) IV on Days 3, 5, 7, 9, 11, and 13 (Table 4). If DSA reduction therapy occurs on the same day as investigational product dosing, investigational product will be administered after completion of the plasmapheresis, plasma exchange or immune adsorption treatment session and dosing of the sucrose-free IVIg.

Table 4 Investigational Product Dosing Day, Volume and Amount

	Volume	CINRYZE	Placebo
Day 1	100 mL	5000 Units of CINRYZE (50 mL of CINRYZE/ 50 mL of normal saline)	100 mL of normal saline
Day 3, 5, 7, 9, 11, and 13	100 mL	2500 Units of CINRYZE (25 mL of CINRYZE/ 75 mL of normal saline)	100 mL of normal saline

Note: All doses must be brought up to 100 mL

Additionally, if a study subject has resolution of their qualifying episode of acute AMR and, during the first 180 days after the biopsy of the qualifying episode of AMR, has a new episode of AMR as defined in Section 3.1, the subject may be retreated with investigational product per the same randomization assignment per protocol.

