- Central Hematology prior to administration of investigational product
- Central Clinical chemistry (includes BUN and creatinine) and local BUN and serum creatinine with eGFR_{MDRD} prior to administration of investigational product
- Central lab blood collection for pharmacokinetic/pharmacodynamic analysis prior to the start of DSA reduction therapy (if done), within 15 minutes prior to the start of investigational product infusion, and 1 hour (+5 minutes) after start of investigational product infusion
- Donor-specific antibody reduction treatment and sucrose-free IVIg (plasmapheresis, plasma exchange, or immune adsorption treatments/sucrose-free IVIg may be provided as part of standard of care prior to study entry)
- Investigational product administration (after DSA reduction therapy and sucrose-free IVIg, if done)
- Concomitant medications
- Adverse event monitoring
- Renal allograft assessment including: function and failure
- Subject survival status
- Healthcare resource utilization

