## 11. SAFETY ANALYSES

The safety analysis will be performed using the Safety Analysis Set, unless specified otherwise. Safety variables include TEAEs, clinical laboratory variables, vital signs, lower extremity exam, and C1 INH antibody variables. For each safety variable, the last value collected prior to the first dose of investigational product during the study will be used as baseline for all analyses of that safety variable.

Summary statistics and changes from baseline to post-baseline for clinical laboratory testing, vital signs, diabetes status, and lower extremity exam by treatment group will be presented. For the clinical laboratory testing results, only the scheduled central lab data will be included in the summary tables. All unscheduled or local lab data will only be provided in the listing.

Number, severity, and causality of AEs will be summarized by treatment group.

Results of C1 INH antibody testing will be reported for individual subjects and summarized as appropriate.

A Final on-Treatment Assessment (FoTA) is defined as the last valid assessment obtained up to 30 days after the last dose of the investigational product during the study.

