## 11.2 Clinical Laboratory Variables

Descriptive statistics for clinical laboratory values (in SI units) and changes from baseline at each assessment time point will be presented by treatment group for the following clinical laboratory variables. Baseline is defined as the last measurement prior to the first dose of investigational product during the study .

**Chemistry**      albumin, alanine aminotransferase, alkaline phosphatase, aspartate aminotransferase, blood urea nitrogen (BUN), calcium, spot urine protein, carbon dioxide, chloride, creatinine, calculated eGFR, direct bilirubin, gamma-glutamyl transferase, glucose, lactate dehydrogenase, phosphorus, potassium, sodium, total bilirubin, total cholesterol, total protein, uric acid. Includes also creatinine, calculated eGFR and BUN for time points that do not include a full chemistry panel.

**Hematology**      complete blood count with differential, hematocrit, hemoglobin, platelet count, red blood cell count, white blood cell count with differential.

Clinical laboratory test values are potentially clinically important (PCI) if they meet either the low or high PCI criteria listed in Table 4. The number and percentage of subjects with post-baseline PCI values will be tabulated by treatment group. The percentages will be calculated relative to the number of subjects with available baseline values and at least 1 post-baseline assessment. The numerator is the total number of subjects with at least 1 post-baseline PCI value. A supportive listing of subjects with post-baseline PCI values will be provided including the subject number, site, baseline, and post-baseline values.

All clinical laboratory data will be listed, including pregnancy.

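### A subject taken off treatment after 1 to 5 of the 7 doses has no scheduled post-dose liver or electrolyte panel in that cycle, and the SAP does not settle how the laboratory tables treat that gap

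*Protocol*

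**What the plan says.** Dosing (Protocol 6.2.3): "Eligible subjects in this study will receive a total of 7 doses of investigational product over a 13-day period", on Days 1, 3, 5, 7, 9, 11 and 13.

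Stopping treatment but not the study (Protocol 3.2, repeated in 4.5): "the subject will continue in the study and no Early Discontinuation Visit will be performed". Instead, "the next scheduled treatment visit in the treatment cycle should be conducted and all procedures for that visit should be performed", apart from those tied to study drug. After that, "the scheduled Day 25 post-treatment visit will follow (any remaining treatment visits for that cycle are not required". The Amendment 4 summary gives early collection of safety data after discontinuation as one reason for this rule.

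Chemistry (Protocol 7.1): the full panel is listed at screening, on Day 1 before the first dose, and on Day 13, where the entry begins "Central Clinical chemistry (includes BUN and creatinine". For Days 3 to 11, Day 25, Month 3 onward and the Early Discontinuation Visit, the only serum chemistry listed is BUN and creatinine with eGFR. Protocol 7.2.3.5.1 treats this as a separate test set for visits without the panel.

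Analysis: SAP 11 states that "only the scheduled central lab data will be included in the summary tables"; unscheduled and local results go to listings. For potentially clinically important (PCI) values, SAP 11.2 states: "The percentages will be calculated relative to the number of subjects with available baseline values and at least 1 post-baseline assessment". SAP Table 4 sets PCI limits for ALT, AST, ALP and total bilirubin. SAP 18.3, on repeated or unscheduled assessments, brings every post-baseline assessment into the overall PCI determination.

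**The concern.** Clinical laboratory testing is a named safety endpoint (Protocol 9.9). Protocol 8.2.1 says that experience in this population at this dose is 9 subjects, too few to list expected reactions. Subjects who stop dosing early may include some who stop for a safety reason, yet the schedule takes no liver or electrolyte measurement from them after dosing begins unless the site orders one. If their rate of abnormal values is higher than that of subjects who reach Day 13, the liver tables show too low a percentage. If early stopping differs by arm, the comparison between arms is affected too.

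**Working it through.** No sample-size formula applies; the check is an enumeration of the schedule.

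**Inputs.** Dose days 1, 3, 5, 7, 9, 11, 13 (Protocol 6.2.3): 7 doses, and 5000 + 6 × 2500 = 20,000 U, matching the total in SAP 2.1. Visits kept after a stop: the next treatment visit and Day 25 (Protocol 3.2, 4.5). Visits with a post-dose panel: Day 13 only (Protocol 7.1.2.3). It is drawn before dose 7, so it follows six doses in a subject dosed without gaps.

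**Enumeration**, assuming doses without gaps and a stop decided before the next dosing visit:

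| Doses received | Last dose | Next treatment visit | Scheduled post-dose panel | Post-dose BUN/creatinine |
|---|---|---|---|---|
| 1 | Day 1 | Day 3 | none | Days 3, 25 |
| 2 | Day 3 | Day 5 | none | Days 3, 5, 25 |
| 3 | Day 5 | Day 7 | none | Days 3 to 7, 25 |
| 4 | Day 7 | Day 9 | none | Days 3 to 9, 25 |
| 5 | Day 9 | Day 11 | none | Days 3 to 11, 25 |
| 6 | Day 11 | Day 13 | Day 13 | Days 3 to 13, 25 |

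Five of six early stopping points have no panel. Adding the panel at Day 25 alone would bring this to 0 of 6.

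**Check on the Day 13 input.** In the text version of SAP Table 1 the chemistry tick falls under Day 11. The PK tick, which SAP Table 3 places on Day 13, is displaced in the same way, so I read this as a column shift. Taken literally, a 5-dose stopper would be covered and stops after 1 to 4 doses would not.

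**Study leavers.** Protocol 3.2 sends anyone who leaves before Month 6 to the Early Discontinuation Visit procedures, which include BUN and creatinine but not the panel. A leaver who has already attended Day 13 has a panel. One who leaves earlier does not.

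**Effect on the PCI percentage.** In one arm let n subjects have a baseline, let m have no post-dose liver value, let x have an observed PCI value, and let y be the unobserved PCI cases among the m. Complete data would give (x + y)/n.

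- Denominator read per parameter: the table shows x/(n − m). This is too low whenever y/m > x/(n − m), that is, when those without a value have the higher rate.
- Denominator read as any post-baseline laboratory value: BUN and creatinine keep the subject in, and the table shows x/n. This is too low whenever y > 0.

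SAP 11.2 does not say which reading is meant.

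**Possible scale of m.** The documents give no early-stopping rate. As an assumption, 2%, 5%, 10% or 20% of the planned 56 per arm stopping after 1 to 5 doses gives 56 × 0.02 = 1.1, 56 × 0.05 = 2.8, 56 × 0.10 = 5.6 and 56 × 0.20 = 11.2, or about 1, 3, 6 or 11 subjects without a scheduled value.

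**The case against.** The strongest reply is that these subjects are not lost to safety review. Because no panel is scheduled between Day 1 and Day 13, a subject stopped by Day 9 for a raised ALT must already have had a local or unscheduled ALT. A clinically relevant laboratory change is an AE (Protocol 8.1.6), all AEs are collected to 30 days after the last dose, and AEs leading to study drug withdrawal are tabulated by arm (SAP 11.1). Unscheduled and local results are listed, and the DMC receives listings. Protocol 7.2.3.5.1 allows unexpected abnormal values to be repeated, and 8.1.6 asks for follow-up of new abnormalities at the end of treatment. The remaining treatment visits are not required, but neither are they forbidden. Under SAP 18.3 an unscheduled ALT would enter the PCI determination. Early stopping may also be rare: all 18 pilot subjects completed treatment (Protocol 1.3.2), and no subject in the HAE studies discontinued because of an AE (Protocol 1.3.1).

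Most of this stands, and it limits the point to the scheduled panel and the tables built on it. It does not close the gap. Detection would rest on whether a site happened to order a test, and a new abnormality cannot be followed up if it was never measured. SAP 18.3 helps only if it overrides SAP 11, and the SAP does not say so.

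A reader might go further and infer that early stoppers have no post-dose liver values at all, that they vanish from the safety analysis, or that everyone who leaves the study lacks chemistry. The documents support none of these. Unscheduled tests are possible, a retreated subject has later panels, and Day 25 includes central hematology for those who attend it. A leaver who has attended Day 13 has the panel.

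**Conclusion.** The schedule gap is certain in its corrected extent: after 1 to 5 doses, or on leaving the study before Day 13, no post-dose ALT, AST, ALP, bilirubin or electrolyte value is scheduled in that cycle. It rests on Protocol 7.1.2.3 placing the panel on Day 13 and on the stop being decided before the next dosing visit. A subject who misses Day 11 and is stopped only afterwards would have Day 13 as the next visit.

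The analysis consequence is a possibility, not a demonstrated bias. Either reading of the denominator can understate a liver signal, but the documents give neither an early-stopping rate nor any sign that stopping differs by arm. A specific distortion of the percentages cannot be inferred from them. The conflict between SAP 11 and SAP 18.3 is real and needs settling on its own account.

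SAP 17 records that the sponsor discontinued the trial for futility after the first interim analysis, so a change of schedule cannot recover data here. The laboratory summary and PCI tables (14.3.4.1 and 14.3.4.5) are still marked for the abbreviated report in SAP 20, so the SAP part remains live.

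**What to change.** 1. **Protocol 3.2, 4.5 and Table 1.** For a subject stopped before Day 13, run the full central chemistry panel at the retained next treatment visit and again at Day 25. For a subject who leaves the study before Day 13, run it at the Early Discontinuation Visit. Section 7.1.3.6 and Table 2 label that visit as falling between Day 13 and Month 6, so the wording should say that it also serves earlier leavers.
2. **SAP 11.2, 11 and 18.3.** Make the PCI denominator parameter-specific: subjects with a baseline and at least one post-baseline value of that parameter. Report by arm the number of dosed subjects with no post-dose value for each liver parameter, so that a missing test is not read as a normal one. State in both SAP 11 and SAP 18.3 whether unscheduled and local values enter the PCI table.

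Item 1 needs no extra visit, because blood already goes to the central laboratory at each of these visits, and it does not alter dosing or when treatment is stopped. Its cost is slightly more blood and assay expense for the few who stop early. Item 2 needs no new data. Only item 2 still affects this trial's report; item 1 would matter for any later use of the schedule.

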3.3 Sites and Regions

Approximately 40 sites in approximately 6 countries are expected to participate in this study in North America and Europe.

4. STUDY POPULATION

Each subject must participate in the informed consent process and provide written informed consent/assent before any procedures specified in the protocol are performed. Local laboratory testing will be used to determine subject eligibility.

4.1 Inclusion Criteria

To be eligible for this protocol, a subject must:

1. Be ≥ 18 and ≤ 70 years of age.
2. Weigh ≥ 45 kg with a body mass index (BMI) < 35 kg/m² at screening.
3. Have HLA DSA identified at the time of diagnosis of AMR. If it is anticipated that the local DSA results will not be available within the screening period, previously obtained local DSA results can be used to assess eligibility, if obtained after kidney transplant and within 30 days prior to the qualifying AMR episode. In any instance, a local DSA test should still be performed at the time of AMR diagnosis.
4. Have a first qualifying episode of AMR in the subject's current renal allograft between 72 hours and 12 months after transplant defined by a renal allograft biopsy demonstrating neutrophil and/or monocyte infiltration in the PTC and/or glomeruli with or without evidence of C4d deposition by immunohistopathology according to 2013 Banff criteria.
5. Have achieved adequate renal function defined as: Pre-AMR baseline eGFR_{MDRD} ≥ 20 mL/min/1.73m² for a qualifying AMR episode occurring ≤ 21 days after transplant or pre-AMR baseline eGFR_{MDRD} ≥ 30 mL/min/1.73m² for a qualifying AMR episode occurring > 21 days after transplant. The pre-AMR baseline is the highest eGFR_{MDRD} value obtained following the kidney transplant and within 30 days prior to the qualifying AMR episode. If more than 1 eGFR_{MDRD} value is available, a mean of the 2 highest values (at least 1 day apart and both prior to the AMR episode) will be used as the pre-AMR baseline value. If no eGFR_{MDRD} was obtained within 30 days prior to biopsy, it can be evaluated within a 60 day period.
6. Receive first dose of investigational product after 7 days after the kidney transplant procedure and within 7 days after the qualifying renal allograft biopsy procedure that was positive for AMR.
7. Be informed of the nature of the study and provide written informed consent before any study-specific procedures are performed.
8. If female and of child-bearing potential, must have a negative urine pregnancy test confirmed by a negative serum beta human chorionic gonadotropin (beta-HCG) pregnancy test at the Screening Visit and must have a negative urine pregnancy test at the Day 1 visit.
9. Agree to comply with any applicable contraceptive requirements of the protocol.

4.2 Exclusion Criteria

Subjects are excluded from the study if any of the following exclusion criteria are met:

1. Have received pediatric en bloc kidney transplant.
2. Have primary Focal Segmental Glomerulosclerosis, rapidly progressive glomerulonephritis, membranoproliferative glomerulonephritis type 1 (including C3 glomerulopathy), “dense deposit disease”, or thrombotic microangiopathy as the cause of native kidney failure.
3. Have prior or concurrent non-renal solid organ transplant or hematopoietic stem cell transplant (HSCT) or have more than 2 completed kidney transplant procedures (note: 1 double kidney transplant procedure is considered to be 1 procedure).
4. Have a known neoplastic lesion in the transplanted allograft
5. Have, any ongoing infection that causes hemodynamic compromise or as determined by the investigator, any surgical or medical condition that could interfere with the administration of investigational product, interpretation of study results, or could compromise patient safety, including (as determined by the transplanting surgeon and documented in the operative report) any major technical complications of the renal artery, renal vein, or ureteral anastomosis
6. Have ongoing treatment for HCV infection.
7. Have had a recent myocardial infarction (MI) within the past 6 months and/or at the time of screening are treated with anticoagulants and/or antiplatelet agents (excluding aspirin) for a previous myocardial infarction.
8. Have a history of:
 - abnormal bleeding,
 - clotting events or disorders (excluding a history of clotted hemodialysis access or superficial thrombophlebitis in the absence of medically confirmed coagulopathy),
 - any coagulopathy (documented or clinically suspected)

For example, patients should be excluded if they have a history of renal allograft arterial or venous thrombosis, deep vein thrombosis, pulmonary embolism, ischemic cerebrovascular accident (stroke) or transient ischemic attack (TIA), any large vessel thrombosis.

9. Have a history of allergic reaction to CINRYZE or other blood products.
10. Have had any change in androgen therapy (eg, danazol, oxandrolone, stanozolol, testosterone), tranexamic acid, epsilon-aminocaproic acid, or other fibrinolytics within 3 months before the first dose of investigational product.
11. Have participated in the active dosing phase of any other investigational drug study within 30 days prior to dosing with investigational product.
12. Have any of the following local laboratory values reported prior to dosing with investigational product:
 - Within 24 hours prior to subject dosing, white blood cell (WBC) count $<0.5 \times 10^9/L$ or $>20 \times 10^9/L$ (the value of $>20 \times 10^9/L$ should be excluded if obtained during steroid treatment)
 - Within 24 hours prior to subject dosing platelet count $< 25 \times 10^9/L$ or $>600 \times 10^9/L$

13. Be pregnant or breastfeeding.
14. Have received any of the following agents within 1 month prior to the first dose of investigational product:
 - Sucrose-containing IVIg
 - Any C1 INH (plasma-derived [eg, CINRYZE[®], Berinert[®], Ceter[®]] or recombinant [eg, Rhucin[®]])
 - Eculizumab (Soliris[®])
 - Ecallantide (Kalbitor[®])

